#### 4. STUDY DESIGN

#### 4.1 Overall Design

This will be an open-label randomized clinical trial at an academic tertiary care center comparing oral ferrous sulfate to intravenous (IV) ferumoxytol in pregnant women with IDA in the second or third trimester.

#### 4.2 Justification for Dose

Historically, oral ferrous sulfate has been increased up to 2-3 tablets daily for anemia. However, this practice as come into question as women often have difficulty with completing oral treatment due to gastrointestinal side effects. Immediate release oral iron products are preferred for treatment of iron deficiency anemia; enteric coated and slow/sustained release preparations are not desired due to poor absorption (Hershko 2014; Liu 2012).

Further, there is increasingly more and more evidence optimal oral iron absorption occurs with single dosing every other day (Stoffel, et al 2020). There is also evidence to demonstrate intermittent dosing is also associated with less adverse side effects (RR 0.41, 95% CI 0.21 to 0.82; 6 studies, 1166 participants; moderate-quality evidence) (Cochrane 2019).

The dosing for intravenous iron was initially based on the Ganzoni formula. However, it was noted to be cumbersome as it was not practical to dose outside of the confines of elemental iron in the viable. Thus in clinical practice patients have received the standard dosing 510 mg x 2 and recently there was an investigation by Auerbach et al which demonstrated the efficacy of single dosing of 1020 mg in a single infusion (MA).

In regards to a pregnancy specific population, it is of particular interest if receipt of intravenous doing can be stratified by hemoglobin level ranges. There is retrospective data that suggests that intravenous iron dosing with respect to pre-pregnancy body mass index may also be an area of future concern.

# 4.3 End of Study Definition

The study will be complete once enrollment has been completed. The goal is 80 patients with 40 in each arm.

#### 4.4 Sample Size

We estimated minimum sample size required for 90% power, one-sided  $\alpha$ =0.025, and estimated effect sizes for the outcomes of change in proportion of women (Hg <11g/dL) by birth hospitalization based on the findings of previous studies. Based on these parameters and allowing for 20% drop-out rate, the study requires 32 subjects per arm. The analysis plan and sample size calculation were developed in consultation with Maternal-Fetal Medicine Senior

Biostatistician, [name] (Co-I). We plan to recruit 80 patients to account for potential loss to follow up.

#### 4.5 Timeline

Aim 1 Milestones	Q1	Q2	Q3	Q4
Extramural funding application preparation and submission. Letter of intent submitted to PCORI February 4 th ; full applications due May 5 th .	X			
Patient screening and enrollment. Patients identified via CBC testing during the second trimester				
Randomization. Patients randomized to IV iron cohort or Oral iron cohort	X			
Intervention. IV iron cohort receives intravenous iron. Oral iron cohort prescribed ferrous sulfate tablets.		X	X	
Data Analysis and Manuscript Preparation and Submission.			X	X

### 5. STUDY POPULATION

# 5.1. Screening and Inclusion/Exclusion Criteria

General Screening guidelines

- I. We will recruit Stanford Children's Health prenatal patients via screening by second trimester complete blood count results, which are routinely performed to screen for anemia performed at 24-28 weeks' gestation or may be performed for any other clinical indication, and with plans for delivery at LPCH. Patients can be included in the study up until 34 weeks.
  - a. Patients will be eligible for the study if they meet the following criteria for IDA: hemoglobin 7-10.9 g/dL and serum ferritin  $<30 \mu g/L$ ) (WHO).
  - b. Patients on prenatal supplements with iron and/or taking oral iron in the early part of pregnancy but meeting other inclusion criteria will also be included in the study cohort.
- II. Patients will be screened by chart review
  - a. Patients will need to complete iron studies to appropriately determine eligibility
  - b. Data obtained from the screening process includes a review of CBC screening at performed in the second trimester.
  - c. Review will also include pregnancy dating information using the initial ultrasound, and other medical history information taken at the first prenatal visits. Other baseline information, including such items as contact information, vitals, demographic and pregnancy history information, concomitant medications, and lifestyle information will be reviewed to assess suitability for study participation.

d. Gestational age must be validated prior to enrollment using the latest ACOG criteria that compares LMP derived gestational age with ultrasound parameters. The ACOG criteria for gestational age determination are listed in section is as follows:

**Gestational age assessment** by ultrasonography in the first part of the second trimester (between 14 0/7 weeks and 21 6/7 weeks of **gestation**, inclusive) is based on a composite of **fetal** biometric measurements and has an accuracy of  $\pm$  7–10 days.

#### **5.2 Inclusion Criteria**

Women with a singleton, viable pregnancy greater than 24 weeks gestation based on the best clinical estimate according to ACOG criteria (see below) and have hemoglobin from 7-10.9 g/dL and serum ferritin < 30 ug.

In agreement with ACOG, we recommend that all pregnant women be screened for anemia at the initiation of prenatal care and second/third trimester with a CBC. As this study is focused on intervention in the >24 weeks gestation, we will not be proposing a treatment regimen with IDA identified prior to this time.

Ferritin is also an acute phase reactant and can be elevated in chronic illnesses. Therefore, the study would also include of women with a hemoglobin 7-10.9 g.dL and transferrin saturation < 20%.

#### 5.3 Exclusion Criteria

If the basic screening criteria are met (patient has IDA by parameters outlined above), the next step is to review the exclusion criteria. Those without exclusions should be approached for study participation.

Assess the following exclusions:

- 1. History of hypersensitivity to intravenous iron. Out of an abundance of caution, pregnant women with this history will be excluded due to concern for increased risk of anaphylaxis
- 2. Known hemoglobinopathies. This was added as an exclusion criteria to remove the potential confounder that women with hemoglobinopathies such as sickle cell disease, thalassemia, may have a different physiologic response to intravenous iron.
- 3. History of Inflammatory Bowel Disease or history of gastric bypass surgery. Intravenous iron is the first line for treatment of iron deficiency anemia in individuals with inflammatory bowel disease due to concerns for impaired absorption of oral iron.
- 4. History of Dialysis-Dependent Chronic Kidney Disease (CKD). This category was added as patients with dialysis-dependent chronic kidney disease, because while the initial studies treated CKD patients with Ferumoxytol, these patients would require a complex dose adjustment due to decreased clearance.
- 5. Multifetal pregnancy (twins reduced to singleton or with vanishing twin syndrome prior to 14 weeks qualify)
- 6. Gestational age < 24 weeks (needs ultrasound confirmation)

- 7. High-risk co-morbidities for which treatment may be indicated: if patient with multiple medical problems important to discuss with primary obstetrician prior to enrollment.
- 8. Pt with history of with two or more medication allergies: patient with history of medical allergies can slightly increase the risk of hypersensitivity reactions.
- 9. Severe asthma or eczema
- 10. Pt with the following will need additional review of medical history prior to inclusion:
  - a. Receiving treatment with beta blockers
  - b. Systemic inflammatory disease (rheumatoid arthritis, lupus) or connective tissue disorder
  - c. Severe anxiety
- 11. Medication allergy to Tylenol
- 12. Placenta previa

Women who meet inclusion criteria and do not have exclusion criteria may be approached for the informed consent process.

# 5.4 Screening/Re-screening

Patients may be included in the study up to 34 weeks 6/7 days. If the above inclusion criteria are met and exclusion criteria are absent, patients should be approached for study participation (if not already done) and randomization. All women who have a diagnosis of IDA should have the screening form initiated. The screening number will be generated electronically with REDCap is accessed and participant information is entered.

# 5.5 Gestational Age Determination

Gestational age will be determined by the most recent ACOG criteria with ultrasound required prior to randomization. If no ultrasound examination has been performed previously, one will be performed before the patient is randomized. Only pregnant women with gestational age  $\geq 24$  0/7 weeks will be included.

#### **5.6 Informed Consent Process**

An informed consent must be obtained before entry into the randomized trial. Full disclosure of the nature and potential risks of participating in the trial including the risks of being in the standard care group will be made. All potential participants will undergo the informed consent process as approved by the Institutional Review Board at each participating center. Any woman who is potentially eligible will be told about the study and asked if she is willing to participate. The point in the screening process at which a signed informed consent is required will be prior randomization. The study personnel conducting the informed consent process should emphasize the following study criteria during the informed consent process:

• Patients eligible based on hemoglobin will be offered iron studies if it's not already collected as part of routine prenatal care.

- Randomization to a treatment arm with iron to increase hemoglobin, with 50% chance to be assigned to either arm:
  - One group will receive oral iron
  - One group will receive intravenous iron
- Participants to sign medical release
- American College of Obstetrics and Gynecology recommends oral iron as standard of care and IV iron only for a select few medical indications
- Labs will be drawn 4 and 8 weeks post-initiation (Oral iron)/ post treatment (IV iron) and to evaluate anemia
  - Update: We will no longer perform study draw at 6 weeks postpartum, however, we will document labs performed as part of routine study care postpartum.
- Follow up to occur at clinic appointments or phone/email to evaluate symptoms associated with either treatment

Due to elevated rate of anemia in the Hispanic/Latinx/Latina population we will also have consents available in Spanish, or translators will be available for the consent process. A short form consent may also be used depending on the participant's preferred language.

All women who are considered for participation in the study (consent, decline or ineligible) should have a data entry form and entered into the electronic data system even if not randomized. Women who do not meet IDA criteria at 24-28 weeks screening visit, may be re-screened until such time that they meet exclusion criteria or they reach 34weeks' gestation.

# **5.7 Requesting Medical Release Forms**

In order to obtain medical records from participants, each participant should sign a "Release of Medical Information" form. A signed Release of Medical Information form should be obtained at the time of, and preferably before, randomization. Clinical Site staff will be able to answer any questions about the procedure at the very beginning of their participation in the study. Also, reluctance to supply medical records may serve as a potential "red flag" that a potential participant may be an adherence or retention risk.

If a participant refuses to sign a Medical Release Form, probe for reasons for the refusal. Explain the importance of the records for the study and why they are needed. Some participants may be willing to sign a release that is specific to information needed for a particular outcome. If the participant continues to refuse, note the refusal in the participant's chart and continue to follow them according to the protocol if they consent to contacts and/or visits.

# 5.8 Background and Rationale for Hemoglobin, Serum Ferritin and Transferrin Saturation Cutoffs

In women without comorbidities, a serum ferritin <30 ng/mL can confirm the diagnosis of iron deficiency; levels  $\ge 30$  ng/mL rule out the possibility of IDA. Borderline levels of serum ferritin may be in the range of 30 to 40 ng/mL with chronic illnesses such as diabetes because ferritin is an acute phase reactant.

We will also test for iron studies including ferritin, serum iron, total iron binding capacity (TIBC), and calculation of transferrin saturation (TSAT) if not already collected by primary OB prior to inclusion in study.

**TSAT below 20 percent** can also demonstrate evidence of iron deficiency whether the ferritin level is low or normal. Iron supplements can falsely elevate the TSAT. To avoid this test interference, iron parameters should be drawn after an overnight fast, or the woman should simply be advised to avoid iron-containing foods or supplements to mitigate otherwise falsely elevated TSAT values.

# 5.9 Frequency of Labs

The timing of follow up labs is determined by the expected amount of time a participant should see an increase in hemoglobin. The hypothesis is that 1) intravenous (IV) iron therapy will increase hemoglobin more with IV iron than oral iron over a 4 week period, approximately 0.8 g/dL in the IV group and 0.5g/dL in the oral arm and 2) IV iron will improve anemia at the time of birth admission, 1.5 g/dL for IV iron and 1 g/dL for oral iron supplementation, the standard of careThe estimates are informed from a 2018 study which reflected a 1.5 g/dL increase in hemoglobin by time of delivery in the intravenous group.

The follow up and reassessment is further informed by Micheal Auerbach's et al approach to treatment of IDA in pregnancy.

# **6. RANDOMIZATION AND BASELINE VISIT PROCEDURES**

In participants with IDA prior to 24 weeks' gestation, they can still be included in the study if they meet the inclusion criteria at 24 weeks gestation/ enrollment time frame. If IDA is a new diagnosis at the time of 24-28 weeks gestation, patients meeting the inclusion criteria be included.

In both groups, prenatal data will be obtained at the randomization visit. The randomization visit should occur with timing of lab results availability and prenatal visit if applicable.

Randomization may occur upon confirmation that all exclusion/inclusion criteria are satisfied and after verification of participant consent and HIPAA authorization. Of particular importance, careful consideration will be given the patient's prior history and medications to determine final eligibility and the appropriate study algorithm to follow (see below). Study staff will also verify participant contact information and obtain a Release of Information.

The MFM Research team will review the following before randomization:

- Complete review of all exclusion and inclusion criteria
- Informed consent obtained
- Iron studies and baseline labs to confirm eligibility
- Pre-intervention survey to assess symptoms

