# 1.1.2 Responsibilities

The responsibilities of these individuals are described briefly here:

PI and co-PIs are responsible for ensuring the proper conduct of the study clinic site including recruitment as specified in the protocol and accurate collection of the data. Other specific duties include:

- a. Obtaining and maintaining IRB approval and training for study personnel
- b. Obtaining sufficient study areas for study personnel to interview patients and perform study procedures, including storage of study medication and other study supplies.
- c. Participate in study- related meetings or conference calls
- d. Familiarity and training for REDCap based data entry system by appropriate staff.
- e. Screen potential participants for eligibility and consent them. It is important to ensure the patient's primary obstetric provider agrees to follow the study treatment protocol during pregnancy.
- f. Randomize per protocol to intervention arms both arms to receive medication
- g. Follow participants during the antepartum, delivery and 6 (4-12) weeks postpartum periods: with labs as indicated in the protocol and with pre- and post-intervention surveys to monitor patient symptoms and adverse effects

- h. Facilitate collection of labs at 24-28 weeks gestation (preferred window, but may collect up to 34 complete weeks), labs at 4 and 8 weeks post-initiation of pill for standard group and post-treatment of intravenous iron in the active group and delivery.
- i. Trained research staff will conduct research data abstraction from patient medical records, and conduct participant interviews, pill counts, and other direct participant contact as required by the protocol. Research staff at CTRU, will undergo training to ascertain response to severe adverse outcomes, specifically identification of hypersensitivity reactions to intravenous iron.
- j. Investigators will participate in blinded review of outcomes in order to confirm the primary and other key outcomes.
- k. Maternal outcomes will be ascertained through 6 weeks including a postpartum visit in this window. If unscheduled visits occurred at another facility, obtain medical records release (if one has not already been obtained) to order hospital visit records.

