#### 3.2 Secondary Outcome

Evaluate the

- rate of patients who discontinued treatment,
- the rate of adverse events associated with treatment,
- the need for blood transfusion postpartum
- symptoms of patients before, during, and at the completion of therapy

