Patients in both groups will complete post-intervention surveys at 1 week, 4 weeks, and 8-12 weeks after initiating therapy to monitor symptoms and adverse events.

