# 12.3 Analyses

We will conduct an intent-to-treat analysis to compare the primary and secondary outcomes between the treatment arms. The primary outcome is the mean change in hemoglobin in oral vs IV iron over 4 weeks as well mean change in hemoglobin pre delivery. The primary outcome will be assessed using t-tests. Baseline characteristics between the groups will be compared using t-tests and chi-square tests. If there is an imbalance between the treatment arms, we will use multivariable regression modeling. Differences will be considered statistically significant at P<0.05.

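### The pre-intervention symptom survey belongs to a secondary outcome, but Section 12.3 does not prespecify how it enters the between-arm comparison of symptoms

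*Combined protocol and SAP*

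**What the plan says.** Section 6 lists a "Pre-intervention survey to assess symptoms" among the items reviewed before randomization. Section 1.1.2 describes following participants "with pre- and post-intervention surveys to monitor patient symptoms and adverse effects". After randomization, "Patients in both groups will complete post-intervention surveys at 1 week, 4 weeks, and 8-12 weeks after initiating therapy".

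Section 3.2 lists as a secondary outcome the "symptoms of patients before, during, and at the completion of therapy", separately from the adverse-event rate and the discontinuation rate. Section 12.1 gives another list of secondary endpoints, and symptoms are not on it.

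Section 12.3 covers every secondary outcome in one sentence: "We will conduct an intent-to-treat analysis to compare the primary and secondary outcomes between the treatment arms". It names tests for the primary outcome ("The primary outcome will be assessed using t-tests") and for baseline characteristics, but none for symptoms. On adjustment it says: "If there is an imbalance between the treatment arms, we will use multivariable regression modeling". No covariate and no criterion for imbalance is given. Sections 10 and 10.2 do not say whether a symptom already present at entry counts as an adverse event.

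**The concern.** Symptoms at entry are plausible in this population. Section 5.1 admits "Patients on prenatal supplements with iron and/or taking oral iron in the early part of pregnancy", and Section 2.3.2 quotes nausea of 68% and abdominal pain of about 70% on oral iron. Gastrointestinal side effects of oral iron are part of the rationale in Section 2.2, so a reader will look at the symptom comparison.

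If a woman's symptoms at entry predict her later symptoms, including them in the model removes variation unrelated to treatment. Adjusting only after an imbalance is seen forgoes that gain whenever the arms happen to be balanced. With no stated rule, three analyses also remain open after the data are seen: post-treatment prevalence, change from entry, and new onset. They answer different questions, and this is an open-label trial with patient-reported symptoms.

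**Working it through.** **The plan's own figure.** The documents give no sample size or power for symptoms. The 32 per arm in Section 12.2 concerns the proportion anemic at birth hospitalization. It cannot be reproduced, because the two proportions are not given, and it does not bear on this point.

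**Inputs from the documents.** 40 per arm (Section 4.3); 20% drop-out (Section 12.2), so 40 × 0.8 = 32 per arm with data; P<0.05 (Section 12.3, taken as two-sided).

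**Assumed inputs.** Prevalence at entry b = 20%, 30% or 50%. Persistence p = 90%, 50% or 30%. Onset rates t (oral vs IV) of 70% vs 40%, or 40% vs 15%. The 70% is of the order of the oral-iron rates in Section 2.3.2; the other rates are assumed. A woman whose entry symptom does not persist faces her arm's onset rate.

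**Difference in post-treatment prevalence.** In each arm, prevalence = t + b·p·(1 − t). The difference between arms is therefore (t_oral − t_IV)(1 − b·p), even with perfectly balanced arms. At p = 0.9:
- 70% vs 40%: 30 × 0.82, 0.73, 0.55 = 24.6, 21.9, 16.5 points at b = 20%, 30%, 50%.
- 40% vs 15%: 25 × 0.82, 0.73, 0.55 = 20.5, 18.3, 13.8 points.

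**Power at 40 per arm.** Simulation with 20,000 to 40,000 trials per setting; unadjusted test vs Mantel-Haenszel test stratified by the entry symptom.

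| Onset, oral vs IV | Persistence | Unadjusted, b = 20/30/50% | Stratified, b = 20/30/50% | Gain (points) |
|---|---|---|---|---|
| 70% vs 40% | 90% | 64 / 57 / 42% | 69 / 63 / 49% | 5 / 6 / 7 |
| 40% vs 15% | 90% | 48 / 39 / 25% | 61 / 54 / 39% | 13 / 15 / 14 |
| 70% vs 40% | 50% | 71 / 67 / 59% | 71 / 68 / 60% | 0 / 1 / 1 |
| 40% vs 15% | 50% | 58 / 52 / 41% | 61 / 56 / 44% | 3 / 4 / 3 |

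Simulation error moves single entries by about a point. At 30% persistence the change is about -1 to +1 point.

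**Power at 32 per arm.** At 90% persistence the gain is about 3 to 7 points (70% vs 40%) and about 11 points (40% vs 15%). At 30-50% persistence it is about -2 to +3 points.

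**Outside this grid.** If every entry symptom persists, the gain can be larger: for 38% (the flatulence rate in Section 2.3.2) vs an assumed 10%, with b = 40%, power goes from 34% to 65%. If women whose entry symptom resolves do not redevelop it, stratifying at 50% persistence gains nothing.

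**New-onset analysis alone.** This drops the women who had the symptom at entry. When entry symptoms often resolve and can recur, it discards information: it loses up to about 18 points of power against the unadjusted comparison (30% persistence).

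**A symptom score.** Adjusting for the entry score multiplies the SD by √(1 − ρ²), where ρ is its correlation with the later score. For an assumed difference of 0.5 SD and 40 per arm, power is 61% unadjusted and 65%, 73% and 88% at ρ = 0.3, 0.5 and 0.7.

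**The case against.** A reader might infer that the survey is used in no analysis and that symptoms will be compared unadjusted. The documents do not say so. Section 3.2 puts symptoms before therapy inside a named outcome, Section 12.3 says secondary outcomes will be compared, and its regression clause could reach symptoms. The symptom method is unspecified, which differs from specified and wrong.

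A reader might also infer that the plan will understate the tolerability difference. Under randomization, the difference in post-treatment prevalence is an unbiased estimate of the effect on prevalence. The 30 or 25 points above describe a different quantity, onset among women free of the symptom. Stratifying gains precision but does not turn one quantity into the other.

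The survey instrument is not in the documents. Whether both surveys ask the same items is unknown, and the symptom outcome may concern anemia symptoms that treatment should relieve, for which a new-or-worse count would miss improvement. Section 2.3.2 does not call its rates new onset, and Section 4.2 cites a relative risk of 0.41 for side effects with intermittent dosing, so 70% may be high for an every-other-day schedule.

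All of this stands, and it limits the size and wording of the point. It does not supply the missing rule. An imbalance trigger still gives no precision gain in balanced arms.

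**Conclusion.** The point holds as a gap in prespecification. The pre-intervention survey is collected and its content is part of a secondary outcome, but Section 12.3 assigns it no role, and nothing separates entry symptoms from new ones. Always adjusting is better than adjusting on observed imbalance.

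The gain at 40 per arm is about 4 to 15 points of power if 90% of entry symptoms persist, and about 0 to 5 points if 30-50% persist (about -2 to +3 at 32 per arm). This rests on assumed entry prevalence, persistence and onset rates, so the range should be quoted, not its upper end. The trial is described as a pilot in Section 3.1 and claims no power for symptoms. The primary hemoglobin analysis is unaffected.

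**What to change.** In Section 12.3, state that each surveyed symptom is compared between arms at 1, 4 and 8-12 weeks with a model that always includes the same symptom's pre-intervention value, where the item is on both surveys, whether or not the arms look balanced. Use logistic regression or Mantel-Haenszel for yes/no items and a linear model for a score.

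Report the new-or-worse rate beside it as a supporting tolerability summary, not as the only analysis. For anemia symptoms, also report improvement. Align the secondary-outcome lists in Sections 3.2 and 12.1.

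The cost is wording only, since the survey is already planned. The downside is a negligible loss of precision if entry symptoms do not predict later ones. A woman already at the worst grade of an item cannot count as worse on it, which is another reason to keep the new-or-worse rate in a supporting role.
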